4.8.5 Vital Signs

Respiratory rate (breaths per minute), heart rate (beats per minute), systolic and diastolic blood pressure (mmHg) and body temperature (°C) will be summarised overall and by treatment group at each applicable visit by means of descriptive statistics. Absolute and percentage changes from baseline to each visit after the first IMP dose will also be summarised. The number and percentage of subjects with Normal, Abnormal NCS and Abnormal CS results will be presented.

A shift table will also be provided for the clinical assessment. This will show the shift from baseline to each post-baseline visit, as well as to the worst overall result assessed at any visit after baseline, including unscheduled visits.

Additionally, for the Visit 7 summary, statistics for weight (kg) and BMI (kg/m²) will be presented.

Notes:

- BMI will be computed as weight at Visit 7 (kg) / (height at Visit 1 [m²]);
- Change from baseline for each parameter will be computed using the formula:
$$\text{Change (unit)} = \text{AVAL (unit)} - \text{baseline AVAL (unit)}$$
- Due to CTP amendments and to the corresponding changes in the procedures schedule and due to differences in the schedule of assessments in the local versions of the CTP, not all the subjects have undergone the same sequence of vital sign assessments. All the values collected will be summarised jointly. Considering the presence of a stratified and permuted blocks randomisation, list no imbalance between treatments is expected.

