8.7. EXACERBATION VISIT/CONTACT

Subjects will be trained by the Investigator to recognise signs and symptoms of NCFB pulmonary exacerbations.

At each post-randomisation visit the patient will be reminded about how to recognise symptoms of a NCFB pulmonary exacerbation and instructed to contact the site as soon as they have experienced these symptoms for 24 hours. If feasible, the subject will be asked to attend the clinic at their earliest convenience. If it is not practical for the subject to make an additional clinic visit then relevant information will be collected via phone and the subject will be asked to send a sputum sample to the clinic.

Any episodes of pneumonia during the trial should be considered as severe pulmonary exacerbations and will also require a clinic visit, if feasible.

The Investigator will decide if symptoms represent a NCFB pulmonary exacerbation meeting the protocol-defined criteria or not and on the appropriate course of action.

It will be clinically determined if the subject requires systemic antibiotic therapy (oral or intravenous) in addition to IMP administration or whether IMP administration should be temporarily interrupted (see below). Treatment of a NCFB pulmonary exacerbation will follow current treatment regimens used in the respective participating trial site.

If subjects need to be admitted to hospital for intravenous antibiotics, they should be visited by the research staff for an assessment within 72 hours of admission (where possible). If the subject is admitted to a hospital that is not the investigational site, the assessments should be carried out (where possible) by the admitting hospital under the direction of the investigational site. These assessments will include those collected during exacerbation visits/contacts and will include details regarding any interruption of IMP administration. In these circumstances, every effort should be made to complete all assessments although it is recognised that this might not be possible.

Telephone calls will be made to patients on a weekly basis during a NCFB pulmonary exacerbation until resolution to assess the progression of symptoms to and to determine whether systemic antibiotic treatment is ongoing. A telephone script will be provided to sites and responses to standardised questions will be collected in relevant eCRFs.

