Resolution of a NCFB pulmonary exacerbation is defined as the date of completion of the required course of systemic antibiotic treatment or the Investigator's judgement that the NCFB pulmonary exacerbation has resolved, whichever is later. Exacerbations occurring less than 14 days after the end of a course of systemic antibiotics for a NCFB pulmonary exacerbation will be considered as a single event (see [Section 9.1.5](#)).

IMP administration may be temporarily interrupted during the time of systemic antibiotic treatment due to a pulmonary exacerbation based on the Investigator's judgement; thereafter, the study treatment should restart as soon as possible. Stop date and re-start

date will be recorded in the relevant eCRF. The occurrence of a pulmonary exacerbation does not mandate the discontinuation of the subject from the trial, unless it occurs between Visit 1 and Visit 2 and /or the Investigator believes discontinuation is in the subject's best interest.

The following assessment will be performed at an Exacerbation Visit or Phone contact, and all details of the pulmonary exacerbation have to be recorded:

- start date and duration of all symptoms since the start;
- all symptoms present which support the NCFB pulmonary exacerbation diagnosis;
- all concomitant medications, especially systemic antibiotics;
- physical examinations and vital signs (if attending the clinic);
- date of CCI [REDACTED] and/or days of CCI [REDACTED] (if any);
- measurement and recording of FEV₁ and FVC (if feasible);
- pulmonary exacerbation as AE/SAE according to protocol and followed until resolution, including weekly follow-up phone calls as detailed above;
- collection of CCI [REDACTED] for other antibacterial panels. If subjects are unable to attend the clinic then suitable arrangements will be made to obtain an additional CCI [REDACTED], if feasible.

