9.1.2. PHYSICAL EXAMINATION

At Visit 1 and Visit 7, a physical examination of general body systems will be performed according to current medical standard and site practice. The examination has to include a chest auscultation. Any relevant worsening regarding physical examination results of a subject since Visit 1 should be recorded as AEs in the eCRF (see Section 16).

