9.1.3. VITAL SIGNS

At Visit 1 and Visit 7, vital signs will be recorded according to site practice and before spirometry testing. This will include heart rate, systolic/diastolic blood pressure (measured after at least 5 minutes in the supine position), respiratory rate, and body temperature.

Automatic or manual devices may be used, but the same device should be used for any given subject throughout the trial. The same arm should be used for all measurements.

The Investigator will perform an overall evaluation for safety purposes and the recording will be reported as “normal”, “abnormal clinically significant” or “abnormal not clinically significant”. Abnormalities of clinical significance will be reported as AEs.

Any clinically relevant worsening of vital signs of a subject since Visit 1 should be recorded as AEs in the eCRF (see [Section 16](#)).

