A fully blinded reassessment of trial size and power was undertaken for Promis I based on blinded data as of 15th January 2020 in 342 randomised, ITT population subjects. This evaluation gave a blinded annualised exacerbation rate estimate of 1.024 per year and an over-dispersion estimate of 0.273. For the hypothesised [CCI] reduction in the exacerbation rate with colistimethate sodium, this translates to annual event rate estimates for placebo and colistimethate sodium of 1.2701 vs 0.8256. The current data in Promis I, therefore, suggested that $n=145$ subjects per arm (290 total, unadjusted for dropout) were required to deliver 90% power, as compared to $n=170$ subjects per arm (340 total, unadjusted for dropout) stated in the protocol. Furthermore, the smallest observed reduction in the exacerbation rate with colistimethate sodium that will yield [CCI] in Promis I was computed to be [CCI].

This recalculation of the sample size was further refined to allow for a reduced overall exposure in Promis I arising due to some subjects dropping out of the study before completing 1 year of follow-up. This leads to a requirement for $n=188$ subjects per arm (376 total, adjusted for dropout) to detect a [CCI] reduction in the event rate with 90% power as compared to $n=210$ subjects per arm (420 total, adjusted for dropout) stated in the protocol; and with $n=188$ subjects per arm, the smallest observed rate reduction to yield [CCI] was computed to be [CCI].

It was, therefore, clear from the blinded data accrued in Promis I subjects to January 2020 that the $n=210$ subjects per arm stated in the protocol was unnecessarily high. At worst, the actual number of subjects required in Promis I is $n=188$ per arm (376 total) and this is inclusive of adjustment for the actual dropout rate seen in the trial itself. Given that, at the time of this sample size reassessment, a total of $n=372$ subjects had been randomised into Promis I, it could very reasonably be argued that very few, if any, further subjects were actually required to be randomised into the study to provide the required power to test the hypothesis that inhaled colistimethate sodium significantly reduces the exacerbation rate relative to placebo. Recruitment was, therefore, concluded with 377 randomised subjects.

CONFIDENTIAL

Sponsor:	Zambon S.p.A.	Protocol Number:	Z7224L01
----------	---------------	------------------	----------

4 Statistical Methodology

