4.8.6 Physical Examination Results

Physical Examination findings collected at each visit will be described by treatment group and overall presenting the number and percentage of subjects with Normal, Abnormal NCS and Abnormal CS results for each body system as per the eCRF. Results for other body systems collected, but not specified in the eCRF will be listed only.

A shift table will also be provided. This will show the shift from baseline to each post-baseline visit, as well as to the worst overall result assessed at any visit after baseline, including

CONFIDENTIAL

Sponsor:	Zambon S.p.A.	Protocol Number:	Z7224L01
----------	---------------	------------------	----------

unscheduled visits.

Notes:

- Due to CTP amendments and to the corresponding changes in the procedures schedule and due to differences in the schedule of assessments in the local versions of the CTP, not all the subjects have undergone the same sequence of physical examinations. All the values collected will be summarised jointly. Considering the presence of a stratified and permuted blocks randomisation list, no unbalance between treatments is expected.

4.8.7 12-Lead ECG

The 12-lead ECG overall interpretation at Visit 1 and Visit 7 will be described by treatment group and overall presenting the number and percentage of subjects with Normal, Abnormal NCS and Abnormal CS results. A shift table will also be provided showing the change from baseline to Visit 7, as well as to the worst overall result assessed at any visit after baseline, including unscheduled visits.

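### The worst-result shift column for vital signs and physical examination takes in Exacerbation Visit exams, so its by-arm comparison leans towards the arm with fewer exacerbations

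*SAP*

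**What the plan says.** Protocol v7.0 schedules both assessments twice. Section 9.1.3: "At Visit 1 and Visit 7, vital signs will be recorded according to site practice and before spirometry testing". Section 9.1.2: "At Visit 1 and Visit 7, a physical examination of general body systems will be performed". Visit 1 is the baseline (SAP 4.1.6), which leaves Visit 7 as the one scheduled post-baseline occasion.

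The list of assessments at an Exacerbation Visit or contact (Protocol 8.7) includes "physical examinations and vital signs (if attending the clinic"). Both flow charts (Protocol Appendix 1, SAP 3.3.1) mark the two assessments in the Exacerbation Visit column. Attendance is not compulsory: "If feasible, the subject will be asked to attend the clinic at their earliest convenience". Otherwise the information is taken by phone.

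SAP 4.1.11 restricts unscheduled assessments to listings unless another section says otherwise. Section 4.8.5 does so for the vital signs shift table: "as well as to the worst overall result assessed at any visit after baseline, including unscheduled visits". Section 4.8.6 repeats the rule ("as well as to the worst overall result assessed at any visit after baseline, including" unscheduled ones) and opens with "Physical Examination findings collected at each visit will be described by treatment group and overall". Neither section sets exacerbation exams apart. Both add a note that stratified block randomisation makes imbalance unexpected. The note refers to differences in assessment schedule caused by protocol amendments and local protocol versions.

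**The concern.** A worst-of-all-visits summary rises with the number of looks and with how ill the subject is at each look. Here both depend on the primary efficacy outcome. The exacerbation definition includes fever, wheezing and dyspnoea; the assessments include temperature, respiratory rate and chest auscultation. The extra exams therefore fall when abnormal findings are likely.

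The randomisation note does not answer this. Randomisation balances schedule differences that are fixed independently of treatment. It cannot balance visits triggered by a post-randomisation event that the drug is meant to reduce.

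At stake is how the worst-result column is read. A lower percentage on colistimethate could reflect fewer and less ill-timed exams, and an unfavourable shift on colistimethate could be partly offset in that column.

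**Working it through.** **Inputs from the documents.** SAP 3.9 gives the rates: "this translates to annual event rate estimates for placebo and colistimethate sodium of 1.2701 vs 0.8256", with over-dispersion k = 0.273. The ratio is 0.8256/1.2701 = 0.650, the 35% reduction in the protocol summary. One year of follow-up, two-sided alpha 0.05.

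**The plan's own figure first.** Wald formula for a negative binomial rate ratio:

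n per arm = (1.960 + 1.282)² × [(1/1.2701 + 0.273) + (1/0.8256 + 0.273)] / (ln 0.650)² = 144.1, rounded up to 145.

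This is the SAP's 145 per arm (power at 145 is 90.2%), so the rates and k are read as the SAP intends.

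**Number of looks.** P(at least one exacerbation) = 1 − (1 + k × rate)^(−1/k): 66.4% on placebo, 52.5% on colistimethate. If every exacerbation leads to a clinic visit, mean post-baseline exams are 1 + 1.27 = 2.27 vs 1 + 0.83 = 1.83. At 50% attendance, 44.3% vs 32.4% have at least one exacerbation exam.

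**Effect on the column.** Let p be the risk of an abnormal result at Visit 7 and q the risk at an attended exacerbation exam, both the same in the two arms, and let a be attendance. Then

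P(worst result abnormal) = 1 − (1 − p) × (1 + k × rate × a × q)^(−1/k).

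With p = 10%, q = 50%, a = 100%:

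- placebo: 1 − 0.90 × (1 + 0.273 × 1.2701 × 0.5)^(−1/0.273) = 1 − 0.90 × 0.5568 = 49.9%
- colistimethate: 1 − 0.90 × (1 + 0.273 × 0.8256 × 0.5)^(−1/0.273) = 1 − 0.90 × 0.6763 = 39.1%

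The documents give none of p, q and a. Assumed ranges: p 5–20%, q from p up to 70%, a 50–100%. Differences are colistimethate minus placebo, taken before rounding.

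| p | q | a | Placebo | Colistimethate | Difference (points) |
|---|---|---|---|---|---|
| 5% | 5% | 50% | 8.0% | 6.9% | −1.0 |
| 10% | 10% | 100% | 20.6% | 17.1% | −3.5 |
| 10% | 30% | 50% | 25.3% | 20.3% | −4.9 |
| 10% | 50% | 50% | 33.6% | 26.4% | −7.3 |
| 10% | 50% | 100% | 49.9% | 39.1% | −10.8 |
| 5% | 70% | 100% | 57.1% | 44.5% | −12.7 |

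The first and last rows are the extremes of the grid. Where q = p (rows 1 and 2) the gap comes only from more looks; where q exceeds p it also contains illness at the time of the exam. A simulation at p = 10%, q = 50%, a = 75% agreed with the formula (42.4% vs 33.2%; formula 42.5% vs 33.1%).

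**Offsetting.** With p = 10% on placebo, q = 50% and a = 50%, a true Visit 7 risk of 18.9% on colistimethate would make the two worst-result percentages equal.

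**The case against.** Much can be said for the plan as it stands.

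- The same table shows the shift to Visit 7 by arm, without exacerbation exams, and Protocol 18.4.3 plans Visit 1 and Visit 7 summaries. This stands, and it confines the point to one column.
- Nothing is tested, and no decision depends on the column. This stands.
- Relevant worsening of vital signs or examination is also recorded as an adverse event (Protocol 9.1.2, 9.1.3), and all data are listed. A reader might infer that harm could go unseen; the documents do not support that.
- The SAP says that subjects did not all follow the same sequence of assessments, because of amendments and local versions. Earlier schedules may have had other exams. With one scheduled exam and full attendance, exacerbation exams are 56% vs 45% of post-baseline exams (rate/(1 + rate)); with two scheduled exams they are 39% vs 29% (rate/(2 + rate)). This dilutes the effect but does not remove it.
- The vital signs shift uses normal/abnormal ratings that Protocol 9.1.3 describes for Visits 1 and 7; section 8.7 does not mention them. Inclusion of exacerbation exams follows from the SAP's wording and the flow charts. It should be confirmed against the case report form.
- Having fewer abnormal findings because of fewer exacerbations is partly a true treatment effect, so calling the whole gap spurious would be wrong.
- Bronchospasm and chest tightness are known effects of the drug (Protocol 3.1) and overlap with exacerbation criteria. Dropping exacerbation exams from the worst-result column could remove drug-related respiratory findings. This is a sound argument against replacing the column, but not against adding a second one.

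**Conclusion.** The point holds for the worst-result column of the vital signs and physical examination shift tables. As written, the number and timing of exams feeding that column depend on the exacerbation rate, and the randomisation note does not cover this.

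The direction depends on colistimethate having fewer exacerbations. That is the design hypothesis, and the SAP Addendum describes the primary result as positive. The size is roughly 1 to 13 percentage points at the planning rates with one year of follow-up, over assumed values of p, q and a; the documents do not permit a single estimate. The split between real effect and ascertainment is also unknown.

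A reader might go further in two ways. One is to say that the safety comparison as a whole is biased; the Visit 7 column and the adverse event tables show otherwise. The other is to take about 14 points (66.4% − 52.5%) as the expected distortion. That would require every exacerbation to bring an attended, abnormal exam, with no subject shifted for another reason.

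ECG and blood tests use similar worst or most-extreme rules (SAP 4.8.7, 4.8.4) but are not planned at Exacerbation Visits, so the point does not extend to them.

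**What to change.** In the tables under SAP 4.8.5 and 4.8.6:

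- keep the all-visits worst-result column;
- add a second worst-result column that excludes exams done at Exacerbation Visits;
- add a row with the number of post-baseline exams per arm, split into scheduled, exacerbation and other unscheduled;
- state that the no-imbalance note does not apply to exams triggered by exacerbations;
- label any separate summary of Exacerbation Visit findings as descriptive, because it conditions on a post-randomisation event.

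The cost is one column and one count row per table, with no new data. The Addendum records that the study is unblinded, so output added now would be marked post hoc, as SAP section 1 requires.

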4.8.6 Physical Examination Results

Physical Examination findings collected at each visit will be described by treatment group and overall presenting the number and percentage of subjects with Normal, Abnormal NCS and Abnormal CS results for each body system as per the eCRF. Results for other body systems collected, but not specified in the eCRF will be listed only.

A shift table will also be provided. This will show the shift from baseline to each post-baseline visit, as well as to the worst overall result assessed at any visit after baseline, including

CONFIDENTIAL

Sponsor:	Zambon S.p.A.	Protocol Number:	Z7224L01
----------	---------------	------------------	----------

unscheduled visits.

Notes:

- Due to CTP amendments and to the corresponding changes in the procedures schedule and due to differences in the schedule of assessments in the local versions of the CTP, not all the subjects have undergone the same sequence of physical examinations. All the values collected will be summarised jointly. Considering the presence of a stratified and permuted blocks randomisation list, no unbalance between treatments is expected.

4.8.7 12-Lead ECG

The 12-lead ECG overall interpretation at Visit 1 and Visit 7 will be described by treatment group and overall presenting the number and percentage of subjects with Normal, Abnormal NCS and Abnormal CS results. A shift table will also be provided showing the change from baseline to Visit 7, as well as to the worst overall result assessed at any visit after baseline, including unscheduled visits.

4.8.8 Pregnancy Test

Results from dipstick urine pregnancy tests for women of child-bearing potential will be listed only.

4.8.9 Other Data

All other data collected in the eCRF will be listed only.

4.9 Adjustment for Covariates

The adjusted mean annual NCFB pulmonary exacerbation rate will be estimated by a negative binomial model including treatment, use of stable concomitant therapy with oral macrolides (e.g. azithromycin or erythromycin or clarithromycin: Yes/No) and pooled site, i.e. country, as detailed in Section 4.9.1, as fixed effects and log-time on treatment as an offset. An exploratory model will also be fitted considering the number of NCFB pulmonary exacerbations requiring oral/intravenous antibiotics in the last 12 months prior to study entry. The non-parametric ANCOVA model on ordered score for number of pulmonary exacerbations and on the annualised number of pulmonary CCI will include the same covariates.

The Cox proportional hazard regression model for CCI will include use of stable concomitant therapy with oral macrolides (e.g. azithromycin or erythromycin or clarithromycin: Yes/No) and pooled site, i.e. country, as covariates.

In the analysis of CCI total score and CCI domain scores, a linear mixed model for repeated measures will be applied. This will include treatment, visit, treatment-by-visit interaction, use of stable concomitant therapy with oral macrolides (e.g. azithromycin or erythromycin or clarithromycin: Yes/No) and pooled site, i.e. country, as fixed effects and baseline value as covariate.

The CCI will be analysed by means of an ANCOVA model including treatment, pooled site, i.e. country, and use of stable concomitant therapy with oral macrolides

CONFIDENTIAL

Sponsor:	Zambon S.p.A.	Protocol Number:	Z7224L01
----------	---------------	------------------	----------

(azithromycin or erythromycin or clarithromycin: Yes/No) as fixed effects and baseline value as covariate.

4.9.1 Site Effects

Sites will be pooled into clusters to fit the model in order to avoid estimation issues for too many degrees of freedom and levels with too low numbers of subjects included, considering that the estimated number of sites participating in the trial is approximately 80, the enrolment is competitive, and the total number of randomised subjects is approximately 420.

Given the similarity in geographic characteristics and concomitant treatments used (other than oral macrolides: i.e. bronchodilators, corticosteroids, etc) sites will be pooled into their corresponding countries.

Any change from this strategy will be discussed at the blind review meeting and documented in the Blind Data Review and Analysis Sets Report. In any case, pooling of the sites will not be data-dependent. The choice will be made based on medical consideration about the sites involved in the study.

